### Follow-Up of Adverse Events and Serious Adverse Events

- The investigator is obligated to perform or arrange for the conduct of supplemental measurements and/or evaluations as medically indicated or as requested by the sponsor to elucidate the nature and/or causality of the AE or SAE as fully as possible. This may include additional laboratory tests or investigations, histopathological examinations, or consultation with other health care professionals.
- Once an AE is detected, it should be followed in the AE eCRFs until it has resolved or until it is judged to be permanent; assessment should be made at each visit (or more frequently if necessary) of any changes in severity, the suspected relationship to the study treatment, the interventions required to treat the event, and the outcome.
- When the severity of an AE changes over time for a reporting period (eg, between visits), each change in severity will be reported as a separate AE.

- Updated SAE information will be recorded in the originally completed eCRF and reported to Incyte Pharmacovigilance (in the SAE eCRF) until resolution, stabilization, the event is otherwise explained, or the participant is lost to follow-up.
- Any updated SAE data (including SAEs being downgraded to nonserious) will be submitted to the sponsor (or designee) within 24 hours of receipt of the information.

See [Appendix G](#) for the management of potential Hy's Law cases.

## 9.4. Reporting of Serious Adverse Events

Regardless of suspected causality (eg, relationship to study treatment or study procedures), all SAEs occurring after the participant has signed the ICF through the last safety visit or at least 90 days after the last dose of study treatment *or* until the participant starts a new anticancer therapy must be reported to the sponsor (or designee) immediately, without undue delay but not later than within **24 hours** of obtaining knowledge of its occurrence unless otherwise specified by the Protocol. The investigator will submit any updated SAE data to the sponsor (or designee) immediately, without undue delay but not later than within 24 hours of it being available.

Investigators are not obligated to actively seek SAE information after the safety follow-up visit or 90 days after the last dose of study treatment. If the investigator learns of any SAE, including death, at any time during this period and he/she considers the event to be reasonably related to study treatment or study participation, then the investigator must notify the sponsor (or designee) within 24 hours of becoming aware of the event.

After the initial AE/SAE report, the investigator is required to proactively follow each participant at subsequent visits/contacts. All SAEs will be followed until resolution, stabilization, the event is otherwise explained, or the participant is lost to follow-up (as defined in Section [7.3](#)).

Prompt notification by the investigator to the sponsor regarding an SAE is essential so that legal obligations and ethical responsibilities toward the safety of participants and the safety of a study treatment under clinical investigation are met.

If the SAE is not documented in the RSI of the [parsaclisib IB](#) or the [tafasitamab IB](#) and is thought to be related to the study treatment, the sponsor or its designee may urgently require further information from the investigator for expedited reporting to health authorities. The sponsor or its designee may need to issue an Investigator Notification to inform all investigators involved in any study with the same drug that this SAE has been reported. Suspected unexpected serious adverse reactions will be collected and reported to the competent authorities and relevant ethics committees in accordance with Directive 2001/20/EC or as per national regulatory requirements in participating countries.

The sponsor has a legal responsibility to notify both the local regulatory authority and other regulatory agencies about the safety of the study treatment under clinical investigation. The sponsor will comply with country-specific regulatory requirements relating to safety reporting to the regulatory authority, IRB/IEC, and investigators.

Investigator safety reports must be prepared for suspected unexpected serious adverse reactions according to local regulatory requirements and sponsor policy and forwarded to investigators as necessary.

An investigator who receives an investigator safety report describing an SAE or other specific safety information (eg, summary or listing of SAEs) from the sponsor will review and then file it along with the IB and will notify the IRB/IEC, if appropriate, according to local requirements.

#### **Serious Adverse Event Reporting**

- Information about all SAEs is collected and recorded on the Adverse Event Form in the eCRF.
- The investigator must report within 24 hours of learning of its occurrence any SAE via the EDC system (primary method) or by completing the Serious Adverse Event Report Form in English (only if the EDC system is not available). The contact information for Incyte Pharmacovigilance by email/fax is listed in the Study Reference Manual.
- In circumstances where the EDC system is not accessible for reporting SAE information (initial and/or follow-up SAE information) to the sponsor within 24 hours, refer to the Incyte Reference Guide for Completing the Serious Adverse Report Form. Once the EDC system is functional, the SAE report should be retrospectively added to the EDC system and follow-up should be completed through the EDC. The original copy of the Serious Adverse Event Report Form and the email or facsimile confirmation sheet must be kept at the study site (refer to the Incyte Reference Guide for Completing the Serious Adverse Report Form).
- Follow-up information is also recorded in the eCRF and transmitted to Incyte Pharmacovigilance via the EDC system. The follow-up report should include information that was not provided previously, such as the outcome of the event, treatment provided, action taken with study drug(s) because of the SAE (eg, dose reduced, interrupted, or discontinued), or participant disposition (eg, continued or withdrew from study participation). Each recurrence, complication, or progression of the original event should be reported as follow-up to that event, regardless of when it occurs.

## **9.5. Events of Clinical Interest**

An ECI is an AE (serious or nonserious) that Incyte wishes to document in an organized manner for monitoring or understanding. An ECI does not require rapid communication by an investigator to Incyte unless it meets criteria for rapid communication as an SAE (see Section 9.2).

The following laboratory abnormalities and/or clinical AEs are considered ECIs:

- Tafasitamab:
  - Tumor lysis syndrome
  - IRRs
  - Allergic reactions to study drug  $\geq$  Grade 3
  - CRS
  - Secondary primary malignancy
  - Hepatitis B reactivation
  - Progressive multifocal leukoencephalopathy.

- Parsaclisib:
  - ALT  $\geq 5 \times$  ULN
  - AST  $\geq 5 \times$  ULN
  - Colitis
  - Diarrhea  $\geq$  Grade 3
  - Intestinal perforation
  - Rash  $\geq$  Grade 3
  - Exfoliative dermatitis
  - Pneumonitis
  - PJP infection
  - CMV infection
  - Herpes simplex virus infection
  - Varicella zoster virus infection

#### **9.5.1. Adverse Events of Special Interest**

Not applicable.

#### **9.6. Emergency Unblinding of Treatment Assignment**

Not applicable.

#### **9.7. Pregnancy**

Pregnancy, in and of itself, is not regarded as an AE unless there is suspicion that the study treatment may have interfered with the effectiveness of a contraceptive medication or method. When a pregnancy has been confirmed in a participant during maternal or paternal exposure to study treatment, the following procedures should be followed in order to ensure safety:

- The study treatment must be discontinued immediately (female participants only).
- The investigator must complete and submit the Incyte Clinical Trial Pregnancy Form to the sponsor or its designee within **24 hours** of learning of the pregnancy.

Data on fetal outcome are collected for regulatory reporting and drug safety evaluation. Follow-up should be conducted for each pregnancy to determine outcome, including spontaneous or voluntary termination, details of the birth, and the presence or absence of any birth defects, congenital abnormalities, or maternal and/or newborn complications, by following until the first well-baby visit. Pregnancy should be recorded on a Clinical Trial Pregnancy Form and reported by the investigator to the sponsor or its designee. Pregnancy follow-up information should be recorded on the same form and should include an assessment of the possible causal relationship to the sponsor's study drug to any pregnancy outcome, as well as follow-up to the first well-baby visit or the duration specified in local regulations, whichever is later. Refer to the Incyte Reference Guide for Completing the Clinical Trial Pregnancy Form.

**Any SAE occurring during pregnancy of a study participant must be recorded on the Serious Adverse Event Report Form and submitted to the sponsor or its designee.**

Abnormal pregnancy outcomes (eg, spontaneous abortion, fetal death, stillbirth, congenital anomalies, or ectopic pregnancy) are considered SAEs (if occurring in the study participant) and must be reported as described in Section 9.4. If an abnormal pregnancy outcome is reported in a study participant's partner, the event should be reported to the sponsor on the Clinical Trial Pregnancy Form.

## **9.8. Warnings and Precautions**

Special warnings or precautions for the study drugs, derived from safety information collected by the sponsor or its designee, are presented in the [parsaclisib IB](#) and the [tafasitamab IB](#). Additional safety information collected between IB updates will be communicated in the form of Investigator Notifications. Any important new safety information should be discussed with the participant during the study as necessary. If new significant risks are identified, they will be added to the ICF.

Infection with SARS-CoV-2, the coronavirus that causes COVID-19, is more frequent and severe in patients with hematologic dysfunction ([Jee et al 2022](#)). The presence of hematologic malignancy, baseline neutropenia and lymphopenia, B-cell depletion, and other factors have been identified as risk factors for loss of humoral immunity to COVID-19, poor vaccine response, viral persistence, and severe disease ([Lee et al 2022](#), [Lyudovsky et al 2022](#), [Shree et al 2022](#)). Targeting B-cell function, proliferation, and survival with various therapies are current strategies for improving the outcome of several hematologic malignancies. PI3K $\delta$  inhibition with parsaclisib alone or in combination with other therapies, which may also suppress humoral immunity, has the potential to negatively impact SARS-CoV-2 infection risk, vaccine effectiveness, recovery from COVID-19, and disease severity ([Cheson 2022](#)). Investigators and participants participating in trials of parsaclisib, alone or in combination, need to be aware of these potential risks and consider the local standards of care and available therapies for disease prevention, vaccination, and infection management of COVID-19.

## **9.9. Product Complaints**

The sponsor collects product complaints on study drugs and drug delivery systems used in clinical studies in order to ensure the safety of study participants, monitor quality, and facilitate process and product improvements.

All product complaints associated with material packaged, labeled, and released by the sponsor or its designee will be reported to the sponsor. All product complaints associated with other study material will be reported directly to the respective manufacturer.

The investigator or his/her designee is responsible for reporting a complete description of the product complaint via email or other written communication to the sponsor contact or respective manufacturer as noted in the packaging information. Any AE associated with a product complaint should be recorded as described in Section 9.3.

If the investigator is asked to return the product for investigation, he/she will return a copy of the product complaint communication with the product.

## 9.10. Treatment of Overdose

Overdose is not an SAE unless it meets the criteria of an SAE (see Section 9.3).

Overdose of parsaclisib is defined as any daily dose  $> 20$  mg within the first 8 weeks of the study and  $> 2.5$  mg for the rest of the study within a 24-hour time period ( $\pm 4$  hours).

Overdose of tafasitamab is defined as any dose  $> 120\%$  of the protocol-specified dose per single infusion.

Overdose with concomitant medication will not be recorded in the eCRF unless it resulted in an AE.

In the event of an overdose, the investigator should do the following:

- Contact the medical monitor immediately.
- Closely monitor the participant for any AE/SAE and laboratory abnormalities.
- Obtain a plasma sample for PK analysis if requested by the medical monitor.
- Document the quantity of the excess dose as well as the duration of the overdose in the eCRF.

Decisions regarding dose interruptions or modifications will be made by the investigator in consultation with the medical monitor based on the clinical evaluation of the participant. Incyte does not recommend specific treatment for an overdose; treatment of overdose for either study drug should consist of general supportive measures.

## 10. STATISTICS

### 10.1. Sample Size Determination

Up to 10 evaluable participants will be treated in each of the 5 disease-specific cohorts during the dose confirmation period. Enrollment into a cohort will be halted if the dose is not considered tolerable or once 10 evaluable participants have been treated for 28 days.

If the dose confirmation period for a disease-specific cohort confirms the dose is tolerable, that particular cohort will be opened for enrollment into the dose expansion period. Up to 10 additional participants will be enrolled up to a total of 20 evaluable participants in each of the 5 disease-specific cohorts (up to 100 evaluable participants in the whole study).

With 10 participants in each disease-specific cohort during the dose confirmation period, there is approximately 89.3% probability of observing at least 1 DLT if the underlying DLT rate is 20% and 97.2% probability of observing at least 1 DLT if the underlying DLT rate is 30%. If  $\leq 1$  of 10 participants in each disease-specific cohort during the dose confirmation period experience a DLT, the upper limit of the 95% 1-sided CI for the underlying DLT rate will not be  $> 39.5\%$ . If none of 10 participants experience a DLT in each disease-specific cohort during the dose confirmation period, the upper limit of the 95% 1-sided CI for the underlying DLT rate will not be  $> 25.9\%$ .

With 10 participants in each disease-specific cohort, there is approximately 97.2% probability of observing at least 1 objective response during the dose confirmation period if the underlying

response rate is 30%. For a reference of the precision of the ORR estimate with 10 or 20 participants in each disease-specific cohort, the 2-sided 95% CIs for different observed ORRs ranging from 10% to 100% are provided in [Table 15](#).

**Table 15: Two-Sided 95% Confidence Interval for Different ORR Estimates**

Sample Size	Observed ORR	95% CI
n = 10	10%	(0.3%, 44.5%)
	20%	(2.5%, 55.6%)
	30%	(6.7%, 65.3%)
	40%	(12.2%, 73.8%)
	50%	(18.7%, 81.3%)
	60%	(26.2%, 87.8%)
	70%	(34.8%, 93.3%)
	80%	(44.4%, 97.5%)
	90%	(55.5%, 99.8%)
	100%	(69.2%, 100.0%)
n = 20	10%	(1.2%, 31.7%)
	20%	(5.7%, 43.7%)
	30%	(11.9%, 54.3%)
	40%	(19.1%, 63.9%)
	50%	(27.2%, 72.8%)
	60%	(36.1%, 80.9%)
	70%	(45.7%, 88.1%)
	80%	(56.3%, 94.3%)
	90%	(68.3%, 98.8%)
	100%	(83.2%, 100.0%)

## 10.2. Populations for Analysis

The populations for analysis are provided in [Table 16](#).

**Table 16: Populations for Analysis**

Population	Description
All-screened set	All participants who signed the ICF.
FAS	The FAS includes all participants who received at least 1 dose of study drug. The FAS will be used for the summary of demographics, baseline characteristics, participant disposition, and analyses of all safety and efficacy data.
DLT evaluable set	The DLT evaluable set will include all participants who received at least 3 of 4 doses of tafasitamab and 21 days of treatment with parsaclisib 20 mg QD during the first cycle (28 days) or have experienced a DLT. Participants who are considered not evaluable will be replaced.
Efficacy evaluable set	The efficacy evaluable population includes all participants enrolled in the study who have received at least 1 dose of study drug and completed a baseline scan and meet at least one of the following criteria: 

• <math>\geq 1</math> post baseline scan

• The participant has participated in the study for a minimum of 42 days

• The participant has discontinued from treatment or died prior to the first scheduled postbaseline scan

PK evaluable set	The PK evaluable population will include all participants who received at least 1 dose of study drug and provided at least 1 postdose PK plasma sample.
Immunogenicity analysis set	All participants who received at least 1 dose of study treatment and have at least 1 evaluable anti-tafasitamab antibody (ADA) assessment.

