## 4. STUDY DESIGN

### 4.1. Overall Design

Key elements of the study design are described in [Table 2](#).

The overall objective of this single-arm, open-label, Phase 1b/2a, multicenter basket study is to evaluate whether the anti-CD19 mAb tafasitamab and the PI3K $\delta$  inhibitor parsaclisib can be safely combined at the RP2D and dosing regimen that was established for each of the 2 compounds as a treatment option for adult participants with R/R B-cell malignancies.

The safety, tolerability, PK, and preliminary efficacy of combination therapy with tafasitamab and parsaclisib will be assessed in a dose confirmation period followed by a dose expansion period. Participants will be assigned to 1 of 5 disease-specific cohorts based on the histology of their underlying disease:

- Cohort 1: R/R DLBCL
- Cohort 2: R/R MCL
- Cohort 3: R/R FL
- Cohort 4: R/R MZL
- Cohort 5: R/R CLL/SLL

During the dose confirmation period, participants will be enrolled in 1 of the 5 cohorts in a parallel fashion. Each cohort will enroll 10 evaluable participants, and each participant will be observed for a DLT evaluation period of 1 cycle (28 days). Participants must have received at least 3 of 4 doses of tafasitamab and 21 days of treatment with parsaclisib 20 mg QD during the first cycle (28 days) or have experienced a DLT to be considered evaluable for the dose confirmation period. Participants who are considered not evaluable will be replaced.

An iDSMB will review data once the 10th DLT-evaluable participant from any cohort completes the DLT evaluation period (C1D28 or experiences a DLT). Reviews will be repeated every 4 months thereafter. The occurrence of DLTs in 2 or more of the first 10 DLT-evaluable participants will also trigger iDSMB review of overall safety data and specifics from the case.

The decision to continue enrollment into each of the malignancy subtype cohorts will be based on the frequency of DLTs observed in the first 10 evaluable participants and review of ongoing safety data. After the safety review is completed and the dose confirmation decision is made, the dose expansion period for that cohort will begin, and up to 10 additional participants will be enrolled (up to a total of 20 evaluable participants in each cohort across both study periods; see [Figure 1](#)).

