### **6.5. Dose-Limiting Toxicity and Determination of the Recommended Phase 2 Dose**

#### **6.5.1. Definition of a Dose-Limiting Toxicity**

Dose-limiting toxicity will be defined as the occurrence of any of the toxicities in [Table 7](#) up to and including Day 28 (Cycle 1/Day 28), except those with a clear alternative explanation. All DLTs will be assessed for severity by the investigator using CTCAE v5.0 criteria.

During the DLT evaluation period, participants who receive at least 3 of 4 doses of tafasitamab and 21 days of parsaclisib 20 mg QD or have a DLT will be considered evaluable for the dose confirmation period.

Dose reductions for individual participants may be made based on events observed at any time during the treatment period; however, for the purposes of opening each expansion cohort, decisions will be made based on events that are observed from the first day of study treatment administration through and including the final day of Cycle 1 (Cycle 1/Day 28).

An event clearly associated with the underlying disease, disease progression, a concomitant medication, or comorbidity will not be considered a DLT.

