#### **10.4.1. Safety Analyses**

Safety analyses will be conducted for the FAS.

Adverse events will be coded by the MedDRA dictionary, and TEAEs (ie, AEs reported for the first time or worsening of a pre-existing event after first dose of study treatment until 90 days after the last dose of study treatment) will be tabulated by preferred term and system organ class for all events, treatment-related events, events of Grade 3 or higher, serious events, fatal events, and events leading to treatment discontinuation or modification. Dose-limiting toxicities will be listed for participants during the dose confirmation period of the study.

Quantitative safety variables and their changes from baseline (laboratory, vital signs, ECG, etc) will be summarized with descriptive statistics. Abnormal values will be flagged and tabulated based on predefined criteria.

The clinical laboratory data will be analyzed using summary statistics. Descriptive statistics of the value and change from baseline at each assessment time will be provided. For laboratory parameters that have CTC grading, shift tables will be provided showing change in CTC grade from baseline to the worst postbaseline grade. In addition, distributions of key laboratory parameters may be plotted over time; these values will also be classified into NCI CTCAE toxicity grades and tabulated.

Descriptive statistics and mean change from baseline will be determined for vital signs at each assessment time. Vital sign results will be reviewed for clinically notable abnormalities.

Descriptive statistics and mean change from baseline will be determined for each ECG parameter at each assessment time. Electrocardiogram results will be reviewed for clinically notable abnormalities. Participants exhibiting clinically notable ECG abnormalities will be listed.

Measures of exposure (eg, days of exposure, dose intensity, etc) of tafasitamab and parsaclisib will be summarized using summary statistics.

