**6. Section 10.2, Populations for Analysis (Table 16: Populations for Analysis)**

**Description of change:** Add a row defining the DLT evaluable set.

**Rationale for change:** This population set will be defined for analyzing DLT results from the dose confirmation part of the study. This population will be more conservative for the calculation of DLT percentage.

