5.3.4. Dose-Limiting Toxicity Evaluable Population

The DLT evaluable population will include participants who have received at least 3 of 4 doses of tafasitamab and 21 days of treatment with parsaclisib 20 mg QD during the first cycle (28 days) or have experienced a DLT. Participants who are considered not evaluable will be replaced.

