10.1. Changes to Protocol-Defined Analyses

A DLT evaluable population was added for analyzing results from the dose confirmation part of the study.

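### The DLT evaluable set is meant for the dose confirmation part but has no period limit, and the planned DLT displays use the FAS instead, so the reported DLT percentage has no fixed denominator.

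*Protocol*

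**What the plan says.** **Definition.** Protocol Table 16: "The DLT evaluable set will include all participants who received at least 3 of 4 doses of tafasitamab", together with 21 days of parsaclisib at the starting dose in Cycle 1; having had a DLT is the alternative route in. SAP 5.3.4 has the same rule: "The DLT evaluable population will include participants who have received at least 3 of 4 doses of tafasitamab". Neither entry mentions a study period.

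**Purpose.** SAP 10.1: "A DLT evaluable population was added for analyzing results from the dose confirmation part of the study". The rationale for item 6 of Protocol Amendment 2 agrees: "This population set will be defined for analyzing DLT results from the dose confirmation part of the study". It adds: "This population will be more conservative for the calculation of DLT percentage". Protocol 4.1 applies the same exposure test, but there it is the condition "to be considered evaluable for the dose confirmation period".

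**What counts as a DLT, and where it is reported.** Protocol 6.5.1 limits DLTs by time, "up to and including Day 28 (Cycle 1/Day 28), except those with a clear alternative explanation", and not by study period. Protocol 10.4.1 says: "Dose-limiting toxicities will be listed for participants during the dose confirmation period of the study". SAP 8.2.4 calls for the number and percentage of participants with a DLT, by cohort. SAP Appendix A assigns both the overall TEAE summary (Table 3.2.1) and the DLT summary (Table 3.2.22) to the FAS. SAP 5.3.2 defines the FAS as everyone who received at least one dose of either drug. SAP 5.2 summarises each cohort by its total only, with no split by period.

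**Sizes.** Protocol 10.1 plans 10 evaluable participants per cohort for dose confirmation, then up to 10 more, for a total of up to 20.

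**The concern.** DLT incidence is a primary Phase 1b endpoint, so its denominator should be fixed by the plan. It is left open in two places.

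First, the set built for this purpose does not carry its purpose in its definition. Expansion participants receive the same regimen from Cycle 1 Day 1, so anyone among them who meets the exposure minimum satisfies the written rule. Protocol 4.1 ties the same test to the dose confirmation period, and that qualifier is missing from the analysis-set definition.

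Second, no DLT display listed in SAP Appendix A uses the set. Tables 3.2.1 and 3.2.22 use the FAS, which spans both periods and also keeps treated participants who were replaced because they were not DLT-evaluable.

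The percentage reported for a cohort could therefore be a dose confirmation figure, a both-periods figure or a mixture. Only the first matches the precision statements in Protocol 10.1. The sponsor added the set to make the percentage more conservative, and a larger denominator without the matching events would do the opposite.

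**Working it through.** **Inputs.** Dose confirmation n = 10 evaluable per cohort, and up to 10 more in expansion (Protocol 10.1). The review trigger is DLTs in at least 2 participants of a cohort (Protocol 6.5.3).

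**The plan's own figures.** The probability of at least one DLT among n participants at true rate p is 1 − (1 − p)^n.

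- p = 20%: 1 − 0.8^10 = 89.26% (stated 89.3%).
- p = 30%: 1 − 0.7^10 = 97.18% (stated 97.2%).

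The exact (Clopper-Pearson) one-sided 95% upper limit for x events in n is the 0.95 quantile of a Beta(x + 1, n − x) distribution.

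- 0/10: 25.89% (stated as not above 25.9%).
- 1/10: 39.42% (stated as not above 39.5%).

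All four figures reproduce, and all rest on n = 10.

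**If expansion participants enter the denominator and no expansion DLT is counted.** The first column is the intended set. The others use the literal definition with 5 or 10 evaluable expansion participants. One-sided 95% upper limits are in brackets.

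| DLTs | n = 10 | n = 15 | n = 20 |
|---|---|---|---|
| 1 | 10.0% (39.4%) | 6.7% (27.9%) | 5.0% (21.6%) |
| 2 | 20.0% (50.7%) | 13.3% (36.3%) | 10.0% (28.3%) |
| 3 | 30.0% (60.7%) | 20.0% (44.0%) | 15.0% (34.4%) |

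Halving needs a full expansion and no expansion DLT counted. Pooling five full cohorts has the same effect: 10/50 = 20% becomes 10/100 = 10%.

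**If expansion DLTs are counted.** The percentage need not fall. Two DLTs in each period give 4/20 = 20%, the same as 2/10. The upper limit is then 40.1% instead of 50.7%, and the figure describes both periods together.

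**On the FAS as now assigned.** Treated participants who are not DLT-evaluable are added as well. Their number is not given. Assuming 2 of them per cohort:

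- Before any expansion: 2/(10 + 2) = 2/12 = 16.7%.
- With full expansion and no expansion DLT counted: 2/(20 + 2) = 2/22 = 9.1%.

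Changing the set definition alone would leave these two figures as they are.

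**Can a cohort with 2 DLTs reach expansion?** Yes. Under Protocol 6.5.3 enrolment in that cohort stops for iDSMB review, but the recommendation is nonbinding and may be to continue unchanged.

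**The case against.** The case on the other side is substantial.

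- **The purpose is stated.** SAP 10.1 and the Amendment 2 rationale both tie the set to dose confirmation. Table 16 also says that non-evaluable participants will be replaced, which Protocol 5.5 links to securing 10 evaluable participants per cohort. A careful programmer would probably read the set as intended. This stands: it is a gap between definition and purpose, not a planned dilution.
- **One-sided dilution is not written down.** A reader might infer that expansion participants enter the denominator while their DLTs are never reported. The documents do not support that as fact. Protocol 6.5.1 limits DLTs by time only, Protocol 10.4.1 describes a listing and does not exclude expansion events, and the set admits anyone who had a DLT. A consistently literal reading puts all DLTs over all evaluable participants; a consistently purposive one keeps both parts to dose confirmation. This stands, so the falling percentages above are conditional.
- **No decision is affected.** Opening a cohort rests on the first 10 DLT-evaluable participants (Protocol 6.5.2), and the review trigger is a count during dose confirmation (Protocol 6.5.3). This stands.
- **No planned table uses the set, and no DLT confidence limit is a planned output.** Both statements are correct. A reader might infer that the plan will publish an upper limit that is too low, but it plans none; the limits in Protocol 10.1 are sample-size statements. The first statement, however, does not remove the problem. The displays use the FAS, which is wider still, and moving them to the set as now defined would leave the period question open.

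**Conclusion.** The concern holds as a mismatch between purpose, definition and display. The set is for dose confirmation, its definition has no period limit, and the DLT count and percentage are assigned to the FAS. The denominator of a primary Phase 1b figure is therefore not uniquely fixed, and it can depart from the n = 10 on which Protocol 10.1 is built.

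The size depends on two things the documents leave open: how many expansion participants a cohort enrols, and whether their DLTs are counted. If they are not counted, 2 DLTs move from 20% to between 13.3% (5 expansion participants) and 10% (10 of them). The last is a halving, and it is the most the set definition allows. On the FAS, treated but non-evaluable participants could lower the figure a little further. If they are counted, the percentage need not fall, but it mixes periods.

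Only the reported result is at risk. The conduct of dose confirmation and the opening of cohorts are untouched. The change is worth making because it carries out the sponsor's stated purpose for a primary endpoint at almost no cost.

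**What to change.** 1. In Protocol Table 16 and SAP 5.3.4, restrict the DLT evaluable set to participants enrolled in the dose confirmation period who meet the existing exposure minimum or had a DLT.
2. In SAP 8.2.4 and Appendix A, assign the DLT count and percentage (the DLT row of Table 3.2.1, and Table 3.2.22) to that set, by cohort. The rest of Table 3.2.1 stays on the FAS.
3. Show any events in expansion participants that meet the DLT definition separately, outside the dose confirmation percentage.
4. Optionally, report the exact one-sided 95% upper limit beside each percentage, so that the result can be read against Protocol 10.1.

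Steps 1 and 2 are both needed: the first alone changes no listed table, and the second alone leaves the period question open. The cost is one phrase in each of two definitions, a population change for one table row and one table, and a separate display if such events occur. No new data are needed and no clinical rule changes.
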